### **E. Blood work**

To collect blood samples, an IV catheter will be placed in the subject's upper limb by a registered nurse. Hence, there will be one needle stick per visit. If an adequate blood sample cannot be accessed using the IV catheter, which happens rarely, with the subject's approval, a singlestick needle blood withdrawal will be performed. However, there will be total of 4 needle sticks including the initial needle stick done to insert the IV catheter applied in a single visit. The recruited registered nurse is an experienced person who is currently working in the ER. She is properly trained in placing IV catheters and drawing blood. A total of 20 mL (4 teaspoons/ 1.3 tablespoons ) of blood will be taken at all pre-and postprandial blood draws, which will be used to assess the levels of hormones via radioimmunoassay kit, blood glucose levels and HbA1c. Blood will be drawn into chilled EDTA tubes (Greiner Vacuette, Monroe, NC) and immediately spun at 1600 x g for 15 minutes at 4°C. Aprotinin (0.6TIU/ml, Phoenix Pharmaceuticals Inc, Burlingame, CA) will be immediately added to the plasma which then will be aliquoted and stored at -80 degrees until assayed for HbA1C, ghrelin, PYY3-36, GLP-1 and insulin. For blood glucose levels, samples will be collected for sodium fluoride containing EDTA tubes (Greiner Vacuette, Monroe, NC). Blood draws will be continuously done at 30 minutes before and 30, 60, 90, 120 and 180 minutes after breakfast consumption. The room has been designed to conduct blood draws.

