### **D. Test Meals**

Four test breakfasts will be matched for energy density, and macronutrient composition (Table 1). Breakfasts will be prepared and assembled onsite at Texas Tech University. Preparing and serving meals will be done in accordance with standardized measures and in compliance with food safety regulations.

Table 1. Macronutrient Composition of Test Breakfasts

	Test Breakfast A-Egg Breakfast	Test Breakfast B- Egg Breakfast with High Saturated Fat	Test breakfast C- Cereal Breakfast	Test Breakfast D-Cereal Breakfast with High Saturated Fat
Energy (kcal)	438	450	447.48	449.6
Protein (g)	22.6	23.4	21.41	22.56
Fat (g)	22.61	24.91	19.55	22
Saturated Fat (g)	5.193	10.893	2.916	10.616
Carbohydrates (g)	44.37	40.45	48.741	41.8
Fiber (g)	10	11.5	7.427	5.667
Glycemic Index	37.48	35.98	55.54	51.52
Glycemic Load	16.63	14.55	27.07	21.53
Weight (g)	328	310	387	352
Energy density (kcal/g)	1.34	1.45	1.17	1.28

Table 2. Contents of Test Breakfasts

A-Egg Breakfast	B- Egg Breakfast with High Saturated Fat	C- Cereal Breakfast	D-Cereal Breakfast with High Saturated Fat
2 Scrambled Eggs	2 Scrambled Eggs	1c Special K RTE High Pro Cereal	1c Special K RTE High Pro Cereal
120 mL Skim Milk	120 mL 2% milk	200 mL Silk Original Soymilk	200 mL Silk Original Soymilk
2 Slices Nature's Own Double Fiber Wheat Bread	2 Slices Nature's Own Double Fiber Wheat Bread	1 Slice [name] Thin Bread	1/2 Slice Arnold Double Protein Whole Grain Bread
30g Margarine	15 g Butter	35g Margarine	15 g Butter
18g Smucker's Strawberry Jam	15g Smucker's Strawberry Jam	10 g Smucker's Sugar Free Strawberry Jam	

Table 3. Flow of Procedures

Group (n=4)	Visit 1	1-7 Days	Visit 2
-------------	---------	----------	---------

Height, weight, waist and hip circumference and blood pressure	x		
Test Breakfast 1 (Part II)	x		
Blood for HbA1c (Part II)	x		
Blood (glucose, insulin, GLP-1, PYY3-36, ghrelin) at 30 min before and 30, 60, 90, 120, 180, min. after breakfast (Part II)	x		x
Food frequency questionnaire (Part I)	x		
Satiety questionnaire at 30 min before and 30, 60, 90, 120, 180 min after breakfast (Part II)	x		x
RMR measurement at 30 min before and 60 and 120 min after breakfast (Part II)	x		
24-hour Recall (Part I)		D1	
Sending images of the pre-and leftovers of all meals including snacks (Part I)		x	
Test Breakfast 2 (Part II)			x

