#### **I. Food Record and 24-hour Recall**

Food record will be maintained by each subject for 7-day period (Appendix G). A 24-hour recall will be collected on the day 1 of the 7 days using Automated Self-Administered 24-Hour (ASA24®) Dietary Assessment Tool.

**Visit 1-** The eligible subjects will come to TTU clinic (Tech Plaza rooms 302 and 305) at about 8 AM after 10 hours fast. Here subjects are allowed to take water. After obtaining informed written consent (Appendix C), anthropometric measurements like weight, height, waist and hip circumferences and blood pressure measurements will be taken (Table 4).

Next, pre-prandial blood sampling will be down 30 minutes prior to test breakfast 1. To retrieve blood samples, an IV catheter will be placed by the registered nurse. Blood draws will be continuously done at 30 before and 30, 60, 90, 120, and 180 minutes after breakfast consumption. Pre-prandial blood draw will be done to assess fasting blood glucose, HbA1c, and hormone levels (i.e. serum insulin PYY, GLP1, ghrelin). Post-prandial blood draws will be done to assess blood glucose and hormone levels. Following pre-prandial blood draw, subjects will be asked to assess their hunger and fullness using the visual analog scale (VAS) (Appendix E). The RMR will be tested for each subject, followed by a standardized test breakfast 1, provided a smartphone and trained to photograph their food intake, using the smartphone provided. The subjects will be asked to consume the entire breakfast in 10 minutes. A food frequency

questionnaire (FFQ) (Appendix F) will be given to assess the egg consumption. RMR will be determined 60 and 120 min post breakfast. Blood draws and VAS administration will be continuously done at 30, 60, 90, 120 and 180 minutes after breakfast consumption. After testing is complete at the 180-minute post-breakfast mark, the subject's IV catheter will be removed.

Subjects will take photos of foods before eating and of the leftovers if any with the help of a smartphone using SmartIntake© app for 7-days. Participants will record all meals for the next 7 days in a food record (Appendix G) as well. On the following day (day 1 of 7 days) a 24-hour recall will be done using Automated Self-Administered 24-Hour (ASA24®) Dietary Assessment Tool.

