**Visit 2-** On day 8, participants will be asked to return with 10 hours fast. As in Visit 1, an IV catheter will be placed by the registered nurse in the subject's upper limb to collect blood for blood glucose, and hormones. Blood will be collected for fasting blood glucose levels and insulin levels PYY, GLP1, ghrelin (as described above) 30 minutes prior to the breakfast. They will be randomized to receive test breakfast 2. Blood draws will be continuously done at 30, 60, 90, 120 and 180 minutes after breakfast consumption. Following each blood draw, subjects will be asked to assess their hunger and fullness using the visual analog scale (VAS) (Appendix E). RMR will be determined 30 mins prior and 60 and 120 min post breakfast.

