## **B. Secondary Outcome Measures:**

1. Difference of subjective hunger level compared between different test breakfasts

This will be measured on visit 1 and 2 after providing test breakfasts.

[Time Frame: Changes in scores (arbitrary units AU) from 30 minutes prior to breakfast to 180 minutes after consumption of test breakfasts (Part II of the study)]

2. Difference of subjective satiety level compared between different test breakfasts

This will be measured on visit 1 and 2 after providing test breakfasts.

[Time Frame: Changes in scores (arbitrary units AU) from 30 minutes prior to breakfast to 180 minutes after consumption of test breakfasts (Part II of the study)]

3. Difference of objective hunger compared between different test breakfasts

This will be measured on visit 1 and 2 after providing test breakfasts by measuring serum ghrelin levels.

[Time Frame: Changes in concentration (area under the curve AUC) from 30 minutes prior to breakfast to 180 minutes after consumption of test breakfasts (Part II of the study)]

4. Difference of objective satiety compared between different test breakfasts using serum Glucagon-like peptide-1 (GLP-1) levels.

This will be measured on visit 1 and 2 after providing test breakfasts by measuring serum GLP-1 levels.

[Time Frame: Changes in concentration (area under the curve AUC) from 30 minutes prior to breakfast to 180 minutes after consumption of test breakfasts (Part II of the study)]

5. Difference of objective satiety compared between different test breakfasts using serum Peptide YY (PYY 3-36) levels

This will be measured on visit 1 and 2 after providing test breakfasts by measuring serum PYY 3-36 levels.

[Time Frame: Changes in concentration (area under the curve AUC) from 30 minutes prior to breakfast to 180 minutes after consumption of test breakfasts (Part II of the study)]

6. Difference of HbA1c levels in high egg consumers as compared to low egg consumers  
This will be measured by taking blood on the visit 1.

[Time Frame: Changes in blood concentration (arbitrary units AU) on visit 1 (Part II of the study)]

7. Difference in Homeostasis Model Assessment-Insulin resistance (HOMA-IR) compared between different test breakfasts

This will be calculated using blood glucose and insulin levels.

[Time Frame: Changes in HOMA-IR values (arbitrary units AU) on visit 1 and 2 after providing test breakfasts (Part II of the study)]

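### HbA1c is listed as an assay on spun, stored plasma, and secondary outcome 7 compares a fasting index (HOMA-IR) between breakfasts after the meal with no sampling time

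*Combined protocol and SAP*

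**What the plan says.** **Specimen handling (E. Blood work).** Blood goes into EDTA tubes and is centrifuged straight away. Aprotinin is then "added to the plasma which then will be aliquoted and stored at -80 degrees until assayed for HbA1C, ghrelin", with PYY3-36, GLP-1 and insulin completing the list. One other tube is described: "For blood glucose levels, samples will be collected for sodium fluoride containing EDTA tubes". No whole-blood or red-cell aliquot is mentioned. The sampling times are given as "Blood draws will be continuously done at 30 minutes before and 30, 60, 90, 120 and 180 minutes after breakfast consumption".

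**Schedule.** Table 3 has a separate row beginning "Blood for HbA1c (Part II", marked at visit 1 only. The visit 1 text says "Pre-prandial blood draw will be done to assess fasting blood glucose, HbA1c, and hormone levels". The visit 2 text says "Blood will be collected for fasting blood glucose levels and insulin levels PYY, GLP1, ghrelin", without HbA1c. Neither the table nor the visit text names a specimen for HbA1c.

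**Attached 40-subject proposal.** Its research plan and budget justification describe HbA1c measured by finger stick with test strips.

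**Outcomes (B. Secondary Outcome Measures).** Outcome 6 is "Difference of HbA1c levels in high egg consumers as compared to low egg consumers", with the time frame "Changes in blood concentration (arbitrary units AU) on visit 1". Outcome 7 compares HOMA-IR between the test breakfasts, computed from glucose and insulin. It is expressed as changes at visits 1 and 2 once breakfast has been given, and no sampling minute is stated.

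**Definition and analysis of HOMA.** Hypothesis 3 (B. Hypotheses) builds the index from fasting glucose and insulin, and Aim 4 groups it with baseline measures. The SAP uses HOMA-IR as a response in the linear regressions on dietary intake. It is not among the six responses listed for the crossover models.

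**The concern.** The two problems are separate.

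First, HbA1c is glycated haemoglobin and sits in red cells, which centrifugation separates from the plasma. This is general assay knowledge; the documents do not state it. A laboratory that followed the Blood work section to the letter would hold plasma that cannot give an HbA1c. It could not recover the value later, because only one HbA1c sample per subject is planned.

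Second, outcome 7 asks what a breakfast does to an index that the protocol elsewhere defines before any breakfast is eaten. As written, the outcome either carries no information about the meal or has no definition. In the second case the sampling time could be chosen after the data are seen.

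**Working it through.** The plan gives no figure to reproduce here. The check sets the texts side by side and counts samples.

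**HbA1c**

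1. Scheduled draws per subject: 1 (visit 1, before breakfast; Table 3 and the visit 1 text). Subjects: 48. Planned values: 1 × 48 = 48 at most.
2. Specimens described in E. Blood work: EDTA plasma after centrifugation (HbA1c, ghrelin, PYY3-36, GLP-1, insulin) and a fluoride tube (glucose). Whole-blood specimens described: 0.
3. Values lost if the text is followed literally: up to 48. Values lost if staff assay whole blood despite the text: 0.
4. Uses of HbA1c: secondary outcome 6, and one of the four glycaemic markers (insulin, glucose, HOMA, HbA1c) in Aim 4, hypotheses 3 and 4, and the SAP regressions. The SAP crosses 3 exposures (energy, saturated fat, eggs) with 4 markers, giving 3 × 4 = 12 associations. HbA1c is the response in 3 of them, and the other 9 are untouched.
5. Outcome 6 time frame: with one draw per subject, the number of within-subject changes is 1 − 1 = 0. The outcome can only be a visit 1 level compared between the two consumer groups.
6. Volume: E. Blood work states 20 mL and already counts HbA1c among its uses, so a whole-blood aliquot needs no additional draw.

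**HOMA-IR**

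1. Glucose and insulin pairs per visit: 6, at −30, 30, 60, 90, 120 and 180 minutes.
2. Pairs that meet the fasting definition in hypothesis 3: 1 (−30 minutes). This sample is taken before that visit's meal, so it cannot reflect that meal. The visit 2 fasting sample, on day 8, follows the first breakfast by about a week of free-living eating. A difference between the two fasting values would show that week and ordinary variation, unless one assumes carry-over from a single breakfast.
3. Pairs taken after the meal: 5. None is fasting, and outcome 7 names none of them.
4. Crossover responses in the SAP: PYY, GLP-1, ghrelin, glucose, insulin and metabolic rate. HOMA-IR does not appear, so the SAP does not settle which sample is meant.

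**Reach**

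- Secondary outcomes affected: 2 of 9 (outcomes 6 and 7).
- Primary outcomes affected: 0 of 6. Outcomes 1 to 4 are dietary. Outcomes 5 and 6 use glucose from the fluoride tube and insulin from plasma, and this point does not question either specimen.

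**The case against.** The HbA1c wording looks like a slip. The same section first speaks of blood being used for HbA1c, and Table 3 separates HbA1c from the hormone row. Laboratory staff would probably keep whole blood anyway. This stands as an account of how the text arose, and it limits the likely harm. It does not remove the instruction, because no other text in the current protocol available for review names a specimen (the consent pages were not available). The finger-stick text does not cure it either. It belongs to the attached 40-subject proposal, so the combined file holds two different methods without saying which applies.

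On outcome 7, the word fasting appears in hypothesis 3, which concerns baseline associations. Outcome 7's own line, like Aim 4, refers only to glucose and insulin levels. On that view the outcome is underspecified rather than contradictory. This is a fair reading, but it leads to the same place: without the fasting definition, outcome 7 has five candidate times, no rule for choosing among them and no model.

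A reader might infer that Aim 4 and hypotheses 3 and 4 fail altogether. They do not, since three of the four markers are unaffected. A reader might also infer from the time frame of outcome 6 that a second HbA1c draw is missing. The outcome line describes a difference between groups and the schedule has one draw, so this is a wording fault with no effect on any computed result.

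**Conclusion.** Both texts are wrong as written and should be corrected. The specimen text matters more, because blood already spun and kept only as plasma cannot be used for HbA1c afterwards. The size of the loss ranges from 0 to all 48 planned values, depending on whether staff follow the wording. The documents do not support saying that the HbA1c data will be lost, only that the written procedure would lose them. That conclusion rests on general knowledge of where HbA1c is carried.

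Outcome 7 is either uninformative about the breakfasts (fasting sample, assuming no carry-over) or undefined (post-meal samples). Little scientific content is at stake, because primary outcomes 5 and 6 already measure the meal response of glucose and insulin, and the SAP regressions already use HOMA-IR.

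**What to change.** 1. **E. Blood work.** Delete HbA1c from the plasma assay list. State that an unspun EDTA whole-blood aliquot from the visit 1 fasting draw is kept for HbA1c, and that this replaces the finger-stick method in the attached 40-subject proposal. Settle this before the first visit 1 blood is processed. If sampling has begun, record which specimen was actually assayed.
2. **Secondary outcome 7.** Remove the comparison of HOMA-IR between breakfasts. Keep visit 1 fasting HOMA-IR for the SAP regressions and leave meal effects to primary outcomes 5 and 6. Alternatively, replace outcome 7 with a named meal-based index, and give its formula, its sampling times and a crossover model in the SAP.
3. **Secondary outcome 6 (minor).** Describe it as the single visit 1 HbA1c level, not as a change.

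The cost is wording in the protocol and SAP, plus one aliquot from a draw already scheduled. No extra visit or draw is needed. The one real downside is that removing or redefining outcome 7 alters the stated list of secondary outcomes, so the change should be documented.

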### **F. Food Frequency Questionnaire**

Food frequency questionnaire (FFQ) adapted from diet history questionnaire (DHQ) by national cancer institute, to identify subjects belonging to quartiles for egg consumption. Number of eggs eaten per week will be determine based on FFQ. This will be given on the first visit.

#### **G. Resting Metabolic Rate**

RMR will be determined using a MedGem® indirect calorimeter as follows: The subject will sit comfortably in a chair wearing a nose clip, and will breathe normally into a mouthpiece. The RMR measurement will take approximately 10 minutes. RMR will be measured 30 minutes pre- and 60 and 120 min post breakfast.

#### **H. Hunger and Satiety Questionnaire**

Hunger and fullness will be assessed using a Visual Analog Scale (VAS) (Appendix E). This will be provided 30 min before and 30, 60, 90, 120, 180 min after breakfast during all the visits.

#### **I. Food Record and 24-hour Recall**

Food record will be maintained by each subject for 7-day period (Appendix G). A 24-hour recall will be collected on the day 1 of the 7 days using Automated Self-Administered 24-Hour (ASA24®) Dietary Assessment Tool.

**Visit 1-** The eligible subjects will come to TTU clinic (Tech Plaza rooms 302 and 305) at about 8 AM after 10 hours fast. Here subjects are allowed to take water. After obtaining informed written consent (Appendix C), anthropometric measurements like weight, height, waist and hip circumferences and blood pressure measurements will be taken (Table 4).

Next, pre-prandial blood sampling will be down 30 minutes prior to test breakfast 1. To retrieve blood samples, an IV catheter will be placed by the registered nurse. Blood draws will be continuously done at 30 before and 30, 60, 90, 120, and 180 minutes after breakfast consumption. Pre-prandial blood draw will be done to assess fasting blood glucose, HbA1c, and hormone levels (i.e. serum insulin PYY, GLP1, ghrelin). Post-prandial blood draws will be done to assess blood glucose and hormone levels. Following pre-prandial blood draw, subjects will be asked to assess their hunger and fullness using the visual analog scale (VAS) (Appendix E). The RMR will be tested for each subject, followed by a standardized test breakfast 1, provided a smartphone and trained to photograph their food intake, using the smartphone provided. The subjects will be asked to consume the entire breakfast in 10 minutes. A food frequency

questionnaire (FFQ) (Appendix F) will be given to assess the egg consumption. RMR will be determined 60 and 120 min post breakfast. Blood draws and VAS administration will be continuously done at 30, 60, 90, 120 and 180 minutes after breakfast consumption. After testing is complete at the 180-minute post-breakfast mark, the subject's IV catheter will be removed.

Subjects will take photos of foods before eating and of the leftovers if any with the help of a smartphone using SmartIntake© app for 7-days. Participants will record all meals for the next 7 days in a food record (Appendix G) as well. On the following day (day 1 of 7 days) a 24-hour recall will be done using Automated Self-Administered 24-Hour (ASA24®) Dietary Assessment Tool.

**Visit 2-** On day 8, participants will be asked to return with 10 hours fast. As in Visit 1, an IV catheter will be placed by the registered nurse in the subject's upper limb to collect blood for blood glucose, and hormones. Blood will be collected for fasting blood glucose levels and insulin levels PYY, GLP1, ghrelin (as described above) 30 minutes prior to the breakfast. They will be randomized to receive test breakfast 2. Blood draws will be continuously done at 30, 60, 90, 120 and 180 minutes after breakfast consumption. Following each blood draw, subjects will be asked to assess their hunger and fullness using the visual analog scale (VAS) (Appendix E). RMR will be determined 30 mins prior and 60 and 120 min post breakfast.

### **Outcome Measures:**

#### **A. Primary Outcome Measures:**

1. Difference of energy intake (kcal) in meals containing eggs as compared to meals that do not contain eggs

Energy intake will be determined using Remote Food Photography Method (RFPM) and the meals of all test subjects will be categorized based on the presence or the absence of eggs in the meals.

[Time Frame: Day 1-7 of the ecological momentary assessment part (Part I) of the study]

2. Difference of energy intake (kcal) in high egg consumers as compared to low egg consumers  
Comparison of mean daily energy intake as measured by Remote Food Photography Method (RFPM) between high egg consumers and low egg consumers identified by providing a food frequency questionnaire (FFQ).

[Time Frame: Day 1-7 of the ecological momentary assessment part (Part I) of the study]

3. Difference of saturated fat (g) intake in meals containing eggs as compared to meals that do not contain eggs

Saturated fat intake will be determined using Remote Food Photography Method (RFPM) and the meals of all test subjects will be categorized based on the presence or the absence of eggs in the meals.

[Time Frame: Day 1-7 of the ecological momentary assessment part (Part I) of the study]

4. Difference of saturated fat (g) intake in high egg consumers as compared to low egg consumers

Comparison of saturated fat intake as measured by Remote Food Photography Method (RFPM) between high egg consumers and low egg consumers identified by providing a food frequency questionnaire (FFQ).

[Time Frame: Day 1-7 of the ecological momentary assessment part (Part I) of the study]

5. Difference of blood glucose levels compared between different test breakfasts

This will be measured on visit 1 and 2 after providing test breakfasts.

[Time Frame: Changes in concentration (area under the curve; AUC) from 30 minutes prior to breakfast to 180 minutes after consumption of test breakfasts (Part II of the study)]

6. Difference of insulin levels compared between different test breakfasts

This will be measured on visit 1 and 2 after providing test breakfasts.

[Time Frame: Changes in concentration (area under the curve; AUC) from 30 minutes prior to breakfast to 180 minutes after consumption of test breakfasts (Part II of the study)]

